6.8.5 Administrative Structure

This trial will be sponsored and managed by Roche S.p.A. The Sponsor will provide clinical operations management, data management, and medical monitoring.

Approximately 50 sites in Italy will participate to enrol approximately 300 patients. Enrolment will be competitive across sites.

Enrolment will occur through an ~~eCRF interactive web-response system (IWRs)~~ or similar system to capture electronically enrolled patients.

~~Accredited~~ Local laboratories will be used for routine monitoring; local laboratory ranges will be *included in eCRF* collected as applicable.

6.9 LIMITATIONS OF THE RESEARCH METHOD

This study will be conducted in approximately 50 sites in Italy and will reflect the standard of care in place in the selected investigational study sites. Therefore, caution should be used in the generalisation of data collected in this study.

Furthermore, the design of the trial may be associated with further limitations. As an example, the possible bias in patients' selection due to the uncontrolled design of the trial may have impact on results.

Finally, pooling of prospective and retrospective data collection will be done even though not equivalent and this needs to be taken into consideration when interpreting the results.

7. PROTECTION OF HUMAN SUBJECTS

7.1 COMPLIANCE WITH LAWS AND REGULATIONS

This study will be conducted in full conformance with the Guidelines for GPP published by the International Society of Pharmacoepidemiology (ISPE) and the laws and regulations of the country in which the research is conducted.

7.2 INFORMED CONSENT

The sponsor's sample Informed Consent Form (and ancillary sample Informed Consent Forms such as a Child's Assent or Caregiver's Informed Consent Form, if applicable) *and the privacy form* will be provided to each site. If applicable, it will be provided in a certified translation of the local language. The sponsor must review and approve any proposed deviations from the sponsor's sample Informed Consent Forms or any alternate Consent Forms proposed by the site (collectively, the "Consent Forms") before IRB/EC submission. The final Consent Forms approved by the IRB/EC must be provided to the marketing authorization holder for archiving and for health authority submission purposes according to local requirements.

The Consent *and* Privacy Forms must be signed and dated by the patient or the patient's legally authorized representative before start of documentation of his or her data in the CRF. The case history or clinical records for each patient shall document the informed consent process and that written informed consent was obtained prior to first documentation of this patient's data in the CRF.

By signing the form, the patient confirms that he/she has been informed about the study and agrees to pseudonymous data collection, pooling of data with similar scientific data (if applicable), and the possibility of monitoring activities. It is the accountability of the physician *for ascertaining that the subject has comprehended the information and to obtain written informed consent from each patient participating in the study, after adequate explanation of the aims, methods, anticipated benefits, and potential hazards of the study. The physician must also explain that the patient is completely free to refuse to enter the study or to withdraw from it at any time, for any reason and without losing the benefit of any medical care to which the patient is entitled or is presently receiving.* A copy of each signed *and dated* Consent Form must be provided to the patient or the patient's legally authorized representative. All signed and dated Consent Forms must remain in each patient's study file or in the site file and must be available for verification by Site Operations Representative at any time.

7.3 INSTITUTIONAL REVIEW BOARD OR ETHICS COMMITTEE

This protocol, the Informed Consent Forms, any information to be given to the patient, and relevant supporting information must be submitted to the IRB/EC by the Site Operations Representative in consultation with the Scientific Responsible and reviewed

and approved by the IRB/EC before the study is initiated. In addition, any patient recruitment materials must be approved by the IRB/EC.

In addition to the requirements for collecting and reporting all AEs, *adverse events of special interest (AES)* and SAEs to the marketing authorization holder, physicians must comply with requirements for AE reporting to the local health authority and IRB/EC.

7.4 CONFIDENTIALITY

The sponsor maintains confidentiality standards by coding each patient enrolled in the study through assignment of a unique patient identification number. This means that patient names are not included in datasets that are transmitted to any marketing authorization holder location.

Patient medical information obtained by this study is confidential and may be disclosed to third parties only as permitted by the Informed Consent Form (or separate authorization for use and disclosure of personal health information) signed by the patient, unless permitted or required by law.

The sponsor, including affiliates, collaborators and licensees may use study data labeled with the patient ID numbers. Study data may also be shared with independent researchers or government agencies, but only after personal information that can identify the patient has been removed. Patients' study data may be combined with other patient's data and/or linked to other data collected from the patients. Patients' study data may be used to help better understand why people get diseases, how to best prevent, diagnose and treat diseases, and to develop and deliver access to new medicines, medical devices, and healthcare solutions to advance patient care.

Medical information may be given to a patient's personal physician or other appropriate medical personnel responsible for the patient's welfare, for treatment purposes.

Data generated by this study must be available for inspection upon request by representatives of national and local health authorities, marketing authorization holder monitors, representatives, and collaborators, and the IRB/EC for each study site, as appropriate.

8. MANAGEMENT AND REPORTING OF ADVERSE EVENTS/ADVERSE REACTIONS

8.1 SAFETY REPORTING REQUIREMENTS FOR STUDIED MEDICINAL PRODUCTS

8.1.1 Safety Parameters and Definitions

The reporting requirements in this section apply to all studied medicinal products. Products are not considered "studied" anymore after the end of the wash out period

following its discontinuation. For safety reporting requirements for non-studied medicinal products, see Section 8.2.

Safety assessments will consist of monitoring and recording SAEs and non-serious AEs (including AEs of special interest), performing safety laboratory assessments, measuring vital signs, and conducting other tests that are deemed critical to the safety evaluation of the study as per standard medical practice.

8.1.1.1 Adverse Events

According to the International Conference of Harmonisation (ICH), an AE is any untoward medical occurrence in a patient or clinical investigation patient administered a pharmaceutical product, regardless of causal attribution. An AE can therefore be any of the following:

- Any unfavorable and unintended sign (including an abnormal laboratory finding), symptom, or disease temporally associated with the use of a medicinal product, whether or not considered related to the medicinal product
- Any new disease or exacerbation of an existing disease (a worsening in the character, frequency, or severity of a known condition), except as described in Appendix 3
- Recurrence of an intermittent medical condition (e.g., headache) not present at baseline
- Any deterioration in a laboratory value or other clinical test (e.g., electrocardiogram [ECG], X-ray) that is associated with symptoms or leads to a change in study treatment or concomitant treatment or discontinuation from study medicine.

8.1.1.2 Assessment of Serious Adverse Events (Immediately Reportable to the Marketing Authorization Holder), Non-serious Adverse Events of Special Interest (AESI) and Other Non-serious Adverse Events

Serious Adverse Events

An SAE is any AE that meets any of the following criteria:

- Is fatal (i.e., the AE actually causes or leads to death)
- Is life-threatening (NOTE: The term “life-threatening” refers to an event in which the patient was at immediate risk of death at the time of the event; it does not refer to an event that hypothetically might have caused death if it were more severe.)
- Requires or prolongs inpatient hospitalization (see A)
- Results in persistent or significant disability/incapacity (i.e., the AE results in substantial disruption of the patient’s ability to conduct normal life functions)
- Is a congenital anomaly/birth defect in a neonate/infant born to a mother exposed to study medicine

- Is a significant medical event in the physician's judgment (e.g., may jeopardize the patient or may require medical/surgical intervention to prevent one of the outcomes listed above)

The terms "severe" and "serious" are not synonymous. Severity refers to the intensity of an AE (e.g., rated as mild, moderate, or severe, or according to NCI CTCAE criteria; see Appendix 3); the event itself may be of relatively minor medical significance (such as severe headache without any further findings).

Severity and seriousness need to be independently assessed for each AE recorded on the CRF (for detailed instructions, see Appendix 3).

Adverse Events of Special Interest AEs of special interest for this study include the following:

- *Tumor lysis syndrome (TLS), irrespective of causality*
- *Second malignancies*
- *Cases of potential medicine-induced liver injury that include an elevated ALT or AST in combination with either an elevated bilirubin or clinical jaundice, as defined by Hy's law (see Appendix 3).*
- *Suspected transmission of an infectious agent by the study medicine, as defined below:*
Any organism, virus, or infectious particle (e.g., prion protein transmitting transmissible spongiform encephalopathy), pathogenic or non-pathogenic, is considered an infectious agent. A transmission of an infectious agent may be suspected from clinical symptoms or laboratory findings that indicate an infection in a patient exposed to a medicinal product. This term only applies when a contamination of the study medicine is suspected

~~Serious IRRs;~~

~~Tumour lysis syndrome (irrespective of regulatory seriousness criteria);~~

~~Serious neutropenia~~

~~Serious infections;~~

~~Hepatitis B reactivation while receiving the appropriate anti-viral therapy.~~

Non-Serious Adverse Events other than Adverse Events of Special Interest

All non-serious AEs (in addition to AEs of special interest) must be collected according to the appropriate level of MedDRA classification.

The physicians are reminded of the possibility to report any adverse reactions (for which they suspect a causal role of a medicinal product) that come to their attention to the

marketing authorization holder of the suspected medicinal product, or to the concerned competent authorities via the national spontaneous reporting system.

The Marketing Authorization Holder is responsible to submit adverse reactions to the competent regulatory authority.

8.1.2 Methods and Timing for Capturing and Assessing Safety Parameters

The physician is accountable for ensuring that all AEs collected as per protocol (see Section 8.1.1.1 for definition) are recorded in the AE section of the CRF and reported to the marketing authorization holder in accordance with instructions provided in this section and in Section 8.1.3.

For each AE recorded in the AE section of the CRF, the physician will make an assessment of seriousness (see Section 8.1.1.2), severity (see Appendix 3), and causality (see Appendix 3).

8.1.2.1 Adverse Event Reporting Period

Qualified *healthcare professionals (HCPs)* will seek information on AEs at each patient contact. All AEs subject to the collecting and reporting requirements outlined in this protocol, whether reported by the patient or noted by study personnel, will be recorded in the patient's medical record and in the AE section of the eCRF.

Once the patient is enrolled in the study, AEs will be collected during the treatment with Obinutuzumab and until 185 days after the last Obinutuzumab dose or until starting a new anti-cancer therapy (whichever occurs first). It includes available data of adverse events that occurred between start of treatment and enrolment in the study (retrospective data collection)..

After this period, AEs that are believed to be related to prior study drug treatment will be collected and should be notified to the competent authority in the Member State where the reactions occurred or to the marketing authorization holder of the suspected medicinal product, but not to both (to avoid duplicate reporting).

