For each patient, the study will consist of a period of 42 months which can include: an induction treatment period (approximately 6 months) in which patients will receive Obinutuzumab and chemotherapy followed by a maintenance treatment period (approximately 24 months) in which patients will receive Obinutuzumab monotherapy and a follow-up period of one year, after the last Obinutuzumab administration. Patients will be followed for 3.5 years after the first treatment administration regardless of early discontinuation of treatment for any reason in any timepoint. Patients who discontinue treatment for reasons other than disease progression (e.g., toxicity, AE) will continue to have their data collected for tumor assessments performed as per clinical practice, until disease progression, withdrawal of consent, study termination by the Sponsor, or death, whichever occurs first, regardless of whether patients start a new anti-cancer therapy.

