6.4.4 Safety Data Collection

Clinical AEs, serious and non-serious, will be recorded in the eCRF during the total observation period, with physician's assessment of severity (mild, moderate, severe or in oncology studies using the National Cancer Institute [NCI] Common Terminology Criteria for Adverse Events [CTCAE]) and relationship to therapy (i.e., related or unrelated) as described in Appendix 3.

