8.1.3 Reporting Requirements from Healthcare Professional to Marketing Authorization Holder

8.1.3.1 Immediate Reporting Requirements from Healthcare Professional to Marketing Authorization Holder

Certain events require immediate reporting to allow the Marketing Authorization Holder and the regulatory authorities to take appropriate measures to address potential new risks associated with the use of the medicine. The HCP must report such events to the marketing authorization holder immediately; under no circumstances should reporting take place more than 24 hours after the HCP learns of the event. The following is a list of events that the HCP must report to the marketing authorization holder within 24 hours after learning of the event, regardless of relationship to study medicine:

- SAEs
- Non-serious AESI
- Pregnancies

The HCP must report new significant follow-up information for these events to the marketing authorization holder immediately (i.e., no more than 24 hours after becoming aware of the information). New significant information includes the following:

- New signs or symptoms or a change in the diagnosis
- Significant new diagnostic test results
- Change in causality based on new information
- Change in the event's outcome, including recovery
- Additional narrative information on the clinical course of the event

For reports of SAEs and non-serious AESI, including follow-up, HCPs should record all case details that can be gathered immediately (i.e., within 24 hours) in the AE page of the CRF and submit the report via the EDC system. A report will be generated and sent to Roche Drug Safety by the EDC system.

In the event that the EDC system is temporarily unavailable, please refer to Section 8.1.3.3.

HCPs must also comply with local requirements for reporting SAEs to the local health authority and IRB/EC.

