^j Response will be collected at mid of the induction (between 10 and 14 weeks after the start of treatments), end of the induction (at the day of cycle 6 until 1 month later) during maintenance (1 year after the start of treatment, i.e. from 10 to 14 months after the start of treatment; 2 years after the start of treatment, i.e. from 22 to 26 months after the start of treatment; 3 years after the start of treatment, i.e. from 34 to 38 months after the start of treatment), at the end of maintenance and at Follow-up as per clinical practice, as well as at any tumor assessment that shows disease progression, CR or CRu during induction or maintenance. The assessment of tumor response will be based on standard Cheson criteria and the Deauville 5-point scale (Appendix 6) (Younes et al. 2017).

^k All adverse events data available in medical records after start of the treatment should be reported until 185 days after the last obinutuzumab dose or until starting a new anti-cancer therapy (whichever occurs first). After this period AEs that are believed to be related to prior study drug treatment will be collected.

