3.3.1 Adverse events

Adverse events are those with start date beyond or equal to the date of first administration of Obinutuzumab and until 185 days after the last Obinutuzumab dose intake or until starting a new anti-cancer therapy (whichever occurs first). After this period AEs that are believed to be related to prior study drug treatment will be collected.

All adverse events will be assigned to a Preferred Term (PT) and will be classified by primary System Organ Class (SOC) according to the MedDRA thesaurus version 22 or higher. Summary statistical tables including frequency counts and percentages and the number of adverse events will be produced.

Data will be listed by study site, patient number, and study day. Events occurring on or after treatment on Day 1 (treatment-emergent adverse events - TEAEs) will be summarized by mapped term, appropriate thesaurus levels, and NCI CTCAE v5.0 grade. In addition, SAEs, including deaths, will be listed separately and summarized.

AEs leading to treatment discontinuation will be listed.

Infusion related reactions (IRRs) and adverse events of special interest (AESI) will be summarized by descriptive statistics and will be listed.

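### The plan gives conflicting end dates for collecting second malignancies (an AESI); if the 185-day/new-therapy window governs, ascertainment over the 42-month follow-up is incomplete and depends on outcome and causality judgement

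*Protocol*

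**What the plan says.** **Passages without an end date, or with a long one**
- Protocol 8.1.1.2 puts "Second malignancies" on the AESI list with no time limit.
- Protocol 8.1.3.1 requires SAEs and non-serious AESIs to be reported "within 24 hours after learning of the event, regardless of relationship to study medicine". That section gives no end date.
- Protocol 6.4.4 states that adverse events "will be recorded in the eCRF during the total observation period".
- Protocol 6.1 sets the length of observation: "Patients will be followed for 3.5 years after the first treatment administration regardless of early discontinuation of treatment". Appendix 2 note b adds that follow-up continues after a new anti-cancer therapy and includes safety data.

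**Passages with the short window**
- Protocol 8.1.2.1 collects adverse events "until 185 days after the last Obinutuzumab dose or until starting a new anti-cancer therapy (whichever occurs first". It then narrows the rule: "After this period, AEs that are believed to be related to prior study drug treatment will be collected".
- The Synopsis, Protocol 6.7.2, Appendix 2 note k, SAP 3.3.1 and SAP Appendix 1 note k carry the same window. None makes an exception for second malignancies.

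**Analysis**
SAP 3.1 and 3.3 define the safety population as all enrolled patients. SAP 3.3.1 plans counts and percentages, with no person-time denominator. SAP 3.4 plans no sensitivity analyses.

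**The concern.** A site that follows 8.1.2.1 would not enter a solid tumour found at month 20 in a patient whose last dose was at month 6, unless the physician attributed it to obinutuzumab. A site that follows 6.4.4 would enter it. The same event could therefore be in or out of the data depending on which section the site reads.

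Under the short window, the time during which unrelated cases are collected also differs between patients for reasons tied to outcome. Progression followed by second-line therapy closes the window at once, and early stopping closes it about six months later. From then on, a case enters only through an individual causality judgement, which the rule in 8.1.3.1 otherwise makes irrelevant for AESIs. A percentage over all enrolled patients does not show that they were observed for unequal times. What is at stake is the interpretability of one AESI in a study whose safety objective is to describe real-world safety. The primary endpoint is not affected.

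**Working it through.** **1. The plan's own figure.** Protocol 6.1 gives about 6 months of induction, about 24 of maintenance and 12 of follow-up: 6 + 24 + 12 = 42 months. This reproduces.

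**2. Window per patient.** 185 / 30.4375 = 6.08 months. Window end = the earliest of last dose + 6.08, start of new therapy, and month 42. Uncovered time = 42 − window end.

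| Case | Window ends (month) | Uncovered (months) | Share of 42 |
|---|---|---|---|
| Last dose at month 30 (full course) | 36.1 | 5.9 | 14% |
| Last dose at month 12 | 18.1 | 23.9 | 57% |
| Last dose at month 6 | 12.1 | 29.9 | 71% |
| New therapy at month 24 | 24 | 18 | 43% |
| New therapy at month 12 | 12 | 30 | 71% |

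**3. Cohort average.** Protocol 6.7.5 supplies an expected POD24 of 13% and a 3-year PFS of 80%. The following are assumptions:
- constant progression hazard up to month 24 and another constant hazard after it;
- no deaths, so every PFS failure is a progression;
- last dose at month 30 or at progression;
- every progressor starts new therapy one month later;
- 0%, 20% or 40% of patients stop early for other reasons, uniformly over months 6 to 30.

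Simulated uncovered share of the 42-month person-time:

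| Other early stopping | 13% progressed by month 24 | 10% progressed by month 24 |
|---|---|---|
| 0% | 22.2% | 20.9% |
| 20% | 27.1% | 25.8% |
| 40% | 31.9% | 30.8% |

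The last column uses the 2-year PFS of 90% that Protocol 6.7.5 also quotes.

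Hand check of the first cell, with progression at the interval midpoints: 0.80 × 36.1 + 0.13 × (12 + 1) + 0.07 × (30 + 1) = 32.7 months covered, and 1 − 32.7/42 = 22%.

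**4. From person-time to cases.** With a constant event hazard, the share of cases missed is the uncovered share times the share of late cases judged unrelated. If 50% to 100% are judged unrelated (assumed), this is 0.22 × 0.5 = 11% up to 0.32 × 1.0 = 32%. The documents give no second-malignancy rate, so no case count follows.

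**5. Which rule governs.** Section 8.1.2.1 is headed as the reporting period, and Appendix 3.3.8 cites it as such for deaths, which favours the short window. Sections 6.4.4 and 8.1.3.1 point the other way, and nothing ranks the sections. If 6.4.4 governed collection, SAP 3.3.1 would still define adverse events by the 185-day window. The same SAP section, however, describes treatment-emergent events with a start and no end.

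**The case against.** The plan sets no 42-month second-malignancy rate as a target. AESIs are to be summarised descriptively and listed by patient and study day. A count within a stated window, plus later related events, is legitimate if presented as that. **This stands in part:** the count is incomplete only relative to the 42-month follow-up, but nothing in the SAP says it will be presented with its window or time at risk.

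Ending general collection at new therapy avoids events that are hard to attribute. **This stands** for general adverse events, and the fix leaves that rule alone.

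Follow-up may be by remote contact, and after treatment stops new therapy and survival status are collected as available (6.5.2). **This stands:** a longer period would improve ascertainment without making it complete.

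A reader might infer more than the documents support:
- *That undercounting is certain.* It is conditional on 8.1.2.1 and SAP 3.3.1 being the rules followed, and late cases judged related still enter the data.
- *That second malignancies are the one AESI needing long follow-up.* Neither document gives latency or incidence.
- *That the either/or choice of recipient in 8.1.2.1 loses late related events.* That clause concerns notification. The same sentence says these events will be collected.
- *That the loss is larger because a fifth of patients start new therapy by month 12.* This puts the entire 3-year PFS shortfall at one year, against an expected POD24 of 13% by month 24.

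**Conclusion.** The passages conflict and should be reconciled. If 8.1.2.1 and SAP 3.3.1 govern, second malignancies are ascertained regardless of causality for only part of follow-up, and the length of that part depends on treatment duration and on progression. The per-patient loss rests only on the plan's timeline: 14% of 42 months for a full course, 71% for a last dose at month 6, and 43% to 71% for new therapy between months 24 and 12.

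The cohort figure of about 22% to 32% rests on the assumptions listed in the working. It would be smaller if some progressors start no new therapy or start it later. Deaths and drop-out would change it as well. The number of missed cases cannot be derived from the documents. This should be corrected, though it does not touch the primary analysis.

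**What to change.** - **Protocol:** reconcile 6.4.4, 8.1.2.1, 8.1.3.1 and Appendix 2 note k. Keep the 185-day/new-therapy window for general adverse events. State that second malignancies are recorded in the eCRF whatever the causality and whatever anti-cancer therapy follows, until month 42 or the end of the patient's follow-up.
- **SAP 3.3.1:** use the same period for this AESI. Report it per patient-year at risk, or as cumulative incidence, split before and after the start of new anti-cancer therapy. SAP Appendix 2 lists no separate AESI output, so add one.

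**Cost:** a protocol amendment, which under Section 3 needs ethics committee approval, at about 50 sites; a change to eCRF wording; and one question at contacts already planned every 3 to 6 months. The scientific downside is harder attribution after second-line therapy. The split presentation handles this by keeping those events visible and separate.
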